## 1.0 Protocol Synopsis

Study Title	MOBILE – ECG Study: Evaluation of the mobiCARE™ ECG Monitoring System Electrode Placement Positioning Limits in a Prospective, Non-Randomized, Single-Center U.S. Study
Sponsor	Seers Technology Company, Ltd.
Principal Investigator	[name]
Study Design	Prospective, non-randomized, single-center, non-significant risk study
Investigational Device	mobiCARE™ Cardiac Monitoring System: Model mobiCARE™ MC200ML. The mobiCARE™ system is a single-channel wearable, mobile and reusable ambulatory ECG recorder that can continuously acquire and store ECG signals using disposable electrodes for up to 9 days. The ECG acquisition for model MC200ML is representative of the other three mobiCARE™ devices: MC200M, MC200M7, and MC200ML7, which differ only by the length of the connector cable length and the battery size. The mobiCARE™-MC200M series is not intended for real-time monitoring.
Gold Standard Device	DR Model TBD Holter Monitor NorthEast Monitoring, Inc. [name]  The Holter Monitor (gold standard) will be used to record Lead II ECG simultaneously to the mobiCARE™ Model MC200ML as a Gold Standard for the purpose of having a simultaneous ECG recording. The Lead II Holter tracing will be used to verify that the heart rhythm identified with the mobiCARE™ device correlates with the heart rhythm identified on the Holter monitor tracing.
Indication for Use	The mobiCARE™ Cardiac Monitoring System is indicated for use on patients who may be asymptomatic or who may suffer from transient symptoms such as palpitations, shortness of breath, dizziness, light headedness, pre-syncope, syncope, fatigue, chest pain and/or anxiety. mobiCARE™ Cardiac Monitoring System is intended for use by patients 18 years or older. The device is not intended for use with critical care patients or for real-time monitoring.
Regulatory Status	This study meets the definition of a non-significant risk (NSR) study. The mobiCARE™ ECG Monitoring Device is a minimal risk device and no medical care decisions will be made based on the measurements. The Seers Technology Co., Ltd. mobiCARE™ ECG Monitoring System is an investigational device in the U.S.
Primary Objective	The primary objective is to quantify the placement accuracy requirements (i.e., how many cm/in. offset may be tolerated from the nominal placement position) needed to ensure appropriate device performance including heart rhythm interpretability and provide rationale to support that such placement accuracy is adequate.
Secondary Objective	The secondary objectives are to: 1. Demonstrate that the device meets the placement accuracy requirements when in normal use, and 2. Identify if there are factors that may impact the placement accuracy and subsequent heart rhythm identification such as age, sex, educational level, BMI, and dexterity.
Primary Endpoint	Evaluation of the ECG signal at the nominal location and in up to three (3) additional standardized locations in each subject to determine if the signal is interpretable. The term “interpretable” is defined as follows: An independent

	
cardiologist is able to identify the ECG rhythm in each location when compared to the ECG rhythm measured in the nominal position of the mobiCARE™ ECG Monitoring System described in the Instructions for Use. ECG rhythm data will be collected for up to two (2) minutes while the patient ambulates.
 
The simultaneous Holter Monitor will be evaluated at the same time points to have a point of reference for the mobiCARE™ system in the case that changes in the rhythm are noted during the study.

Secondary Endpoints (Informational Only)	
 
1. Presence of artifact graded as 1=none, 2=minor (cardiac rhythm is interpretable), or 3=major (cardiac rhythm is not interpretable by the independent cardiologist).
 
2. ECG Morphology measurements: P wave amplitude, QRS amplitude, QRS duration.
 
3. Limited Human Factors Evaluation Measures (n=15): 
 
A. Initial Healthcare practitioner (HCP) placement according to IFU (correct or incorrect placement when referring to the IFU)
 
B. User demonstrates ability to change electrodes (successful or not successful)
 
C. Observe user to determine sufficient dexterity for user to perform the task
 
D. Observe user electrode placement according to skin markings to determine if electrodes are correctly placed.
 
 
 

Participation Duration	Each subject will participate in this study for one (1) visit, for approximately 30 to 60 minutes.
Sites	One (1) investigational site
Population	The study population will include adults who are asymptomatic or who may suffer from transient symptoms such as arrhythmias, palpitations, chest pain or chest pressure; ranging in age, ethnic group, BMI, educational level and gender.
Sample Size	Up to 50 subjects will be consented and enrolled
Eligibility Criteria	
Inclusion Criteria
 
 
1. Male and female adults <math>\geq</math> 18 years of age;
 
2. Willing and able to provide informed consent;
 
3. Able to speak and read English fluently;
 
4. Participant is ambulatory.
 
 
Exclusion Criteria
 
 
1. Patients with cardiac pacemaker;
 
2. Patients with cardioverter defibrillator;
 
3. Patients with other implantable electrical devices;
 
4. Currently has a medical history of skin cancer, rash, skin disorder, keloid, and/or any injury in the chest area;
 
5. Patients with symptomatic episodes where variations in cardiac performance could result in immediate danger to the patient;
 
6. Patients with known history of life-threatening arrhythmias;
 
7. Use in combination with external cardiac defibrillators or high frequency surgical equipment near strong magnetic fields or devices such as MRI;
 
8. Patients with neuro-stimulator, as it may disrupt the quality of ECG data;
 
9. Critical care patients.
 

Enrollment Methodology	
 
1. A minimum of 30% of the study subjects will be <math>\geq</math> 65 years of age to assess the intended use population who may differ in dexterity.
 
2. All ethnic groups, Caucasian, Asian, African American, Hispanic, Other (Pacific Islanders, Native American) will be enrolled.
 
3. BMI range from low to high (defined as BMI <math>>35</math>), will be enrolled.
 

	
4. Male and female subjects with a minimum of 40% of the subjects being female.
 
5. Varied educational levels will be enrolled.

Sponsor Provided Devices	
1. Commercially available single use disposable Ag/AgCl ECG electrodes
 
2. Seers Technology Company Ltd. ECG Monitoring System, Model MC200ML (1 mobiCARE™ ECG Monitoring System per subject)
 
3. Commercially available DR Model TBD Holter ECG Monitor
 
4. Samsung Galaxy A10e Smartphone with WiFi capability only Android device with minimum specifications of OS 7.0 or higher and CPU 1.4GHz or higher
 
5. Skin marking device

Data Management, Biostatistics, Monitoring & EDC	
Eminence Clinical Research, Inc. [name] Main No.: [contact]

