#### 7.1.3 Enrollment

Those who are consented, enrolled, and undergo the ECG readings, and demonstrate the use the application of the electrodes and the ECG on the study subject.

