#### 7.1.4 Enrollment Methodology

The study will include a diverse population to demonstrate the interpretability of ECG heart rhythm tracings obtained by the mobiCARE™ device in various placement locations, as compared to nominal, in a diverse population. Over 30% of the study subjects will be  $\geq 65$  years of age to assess a range of dexterity, all ethnic groups [Caucasian, Asian, African American, Hispanic, (Other (Pacific Islanders, Native American))] will be enrolled. The BMI range from low to high defined as BMI  $>35$ , will be enrolled. Male and female subjects with a minimum of 40% of the subjects being female. Varied educational levels

will be enrolled.

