### 10.5.2 Secondary Endpoints – Informational Only

1. Presence of artifact graded as 1=none, 2=minor (cardiac rhythm is interpretable), or 3=major (cardiac rhythm is not interpretable by the independent cardiologist).
2. ECG Morphology measurements: P wave amplitude, QRS amplitude, QRS duration.
3. Limited Human Factors Evaluation Measures (n=15):
  - A. Initial HCP placement according to IFU (correct or incorrect placement when referring to the IFU)
  - B. User demonstrates ability to change electrodes (successful or not successful)
  - C. Observe user to determine sufficient dexterity for user to perform the task
  - D. Observe user electrode placement according to skin markings to determine if electrodes are correctly placed.

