### What Will Be Required of Study Volunteers?

- You will be required to wear 2 small ECG electrodes that are placed using the adhesive, like what are standard for any ECG heart rhythm monitoring for a portable ECG. A healthcare professional will place the electrodes on the skin of your chest and torso, and you may need to have the area shaved if you have a lot of hair in the location.
- You will also be required to wear 3 other electrodes for another ECG that are also standard for any ECG monitor. This second ECG with 3 electrodes is for a Holter monitor used to record your heart rhythm at the same time the small device with two electrodes records your heart rhythm.
- You will walk a short distance while monitoring your heart rhythm, for 1-2 minutes.
- The 2-electrode portable ECG will then be moved to a 2nd position and on the front of your torso and recorded for 1 to 2 minutes while you walk a short distance; and then a 3rd position and recorded for 1 to 2 minutes while you walk a short distance.
- You will be asked to remove and replace the 2 electrode ECG on the front of your torso at the end of the study and remove them. Then your participation is complete.

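### The 65-and-over quota is set on the whole sample to cover dexterity, but dexterity is scored in only 15 subjects with no stated selection rule or age minimum, so few older users may be scored

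*Combined protocol and SAP*

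**What the plan says.** **The quota.** The enrolment rules in the synopsis (section 1.0) state: "A minimum of 30% of the study subjects will be" at or above "65 years of age to assess the intended use population who may differ in dexterity". Section 7.1.4 repeats the rule in slightly different terms: "Over 30% of the study subjects will be" at or above 65 "years of age to assess a range of dexterity". Both set the percentage on the whole sample, and both give dexterity as the reason.

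**Where dexterity is measured.** Section 10.5.2 lists it under "Limited Human Factors Evaluation Measures (n=15"), together with electrode change and placement by skin markings. Section 11.5.2 keeps the limit of 15 and adds whether the ECG is still interpretable after the user has replaced the device. Appendix 30.3 confirms that the 15 are subjects. The subject form in Appendix 30.3.2 has five tasks rated 1 to 5 by the coordinator, and the average must be at least 3.

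**What is not said.** Neither the sections above nor the schedule of assessment (Table 2) says how the 15 are chosen, sets an age minimum for them, or asks for human-factors results by age.

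**Who does the task.** The recruitment script (Appendix 30.4) tells every volunteer: "You will be asked to remove and replace the 2 electrode ECG on the front of your torso at the end of the study".

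**The concern.** The quota and the measurement it is meant to serve apply to different sets of people. During the primary recordings a healthcare professional positions the device, so those recordings do not test the subject's hands. An older subject outside the 15 counts towards the quota but yields no dexterity score.

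Secondary Objective 2 names both age and dexterity as factors of interest, and section 2.0 says that patients will use the device at home. The margin justification in section 11.4 also relies on patients replacing electrodes at home from skin marks. The subject part of Appendix 30.3.2 is where the study scores that ability. If the 15 include only two or three older users, the study can satisfy its quota and its usability criterion and still say little about the group the quota was written for.

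A pooled average can also hide difficulty in a small subgroup. As an illustration, if 13 younger users score 4 and 2 older users score 1, the mean is (13 × 4 + 2 × 1)/15 = 54/15 = 3.6, which passes.

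**Working it through.** **Inputs from the documents.**
- Quota: 30% aged 65 or over (synopsis; section 7.1.4).
- Human-factors subset: 15 (sections 10.5.2 and 11.5.2; Appendix 30.3).
- Sample size: minimum analysed 37 (section 5.3), planned 44 (section 11.3), maximum enrolled 50 (section 5.3).

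**Assumption.** No selection rule is given, so a simple random draw of 15 is used as a neutral reference case.

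**Step 1: the plan's own figure.** The subset size of 15 has no stated derivation to reproduce. The 37 does. The Farrington-Manning formula with rates 94% and 95%, margin 0.20, one-sided alpha 0.025 and 80% power gives 36.5, so 37, with power 80.6% at 37. Here it serves only as a denominator.

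**Step 2: what the quota guarantees in the subset.** The minimum number of older subjects is 0.30 × N, rounded up. The rest may be under 65.

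| N | 0.30 × N | Minimum aged ≥65 | May be <65 | At least 15 younger? |
|---|---|---|---|---|
| 37 | 11.1 | 12 | 25 | yes |
| 44 | 13.2 | 14 | 30 | yes |
| 50 | 15.0 | 15 | 35 | yes |

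If section 7.1.4's rule is read strictly as more than 30%, the minimum at 50 becomes 16, leaving 34 younger. In every case there are enough younger subjects to fill all 15 places, so the text guarantees no older user in the subset.

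**Step 3: what a random draw would give.** With K older subjects among N, the number X of older users among the 15 is hypergeometric:

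P(X = x) = C(K, x) × C(N − K, 15 − x) / C(N, 15), with mean 15 × K/N.

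For N = 44 and K = 14:
- Mean: 15 × 14/44 = 4.77.
- P(X = 0) = C(30, 15)/C(44, 15) = 155,117,520/229,911,617,056 = 0.00067.

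| N, K | Mean | P(none) | P(≤2) | P(<5) |
|---|---|---|---|---|
| 37, 12 | 4.9 | 0.03% | 4.3% | 40% |
| 44, 14 | 4.8 | 0.07% | 5.7% | 43% |
| 50, 15 | 4.5 | 0.14% | 8.6% | 51% |

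At N = 44, P(≤3) = 19.4%. The 43% chance of fewer than 5 is therefore made up of 19.4% for 3 or fewer and 23.8% for exactly 4.

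**Step 4: how much a given number of older users can show.** If n older users are tested and none fails, the one-sided 95% upper bound on their failure rate is 1 − 0.05^(1/n).
- n = 2: 78%
- n = 5: 45%
- n = 14: 19%

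The plan makes no such inference. The bounds only compare the information in the options.

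**Step 5: the quota applied where it is measured.** 0.30 × 15 = 4.5, so at least 5 of the 15, on either reading of the 30%.

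**The case against.** The best defence has five parts.

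- **Older subjects outside the 15 are not wasted.** This stands. Secondary Objective 2 names age separately from dexterity, and every older subject contributes interpretability, artifact and morphology data. They add nothing on dexterity itself.
- **A subset with no older users is far-fetched.** This stands for random selection: the chance is 0.07% at N = 44, and about 94% of draws contain 3 or more older users. A reader might infer from Step 2 that older users are likely to be missed altogether. The documents do not support that, because they neither describe a selection method that would cause it nor exclude one. The realistic risk is a low number, especially if the first or most convenient 15 are taken.
- **The selection rule may be elsewhere.** Appendix 30.3.1 is attached separately, and the worksheets and electronic case report form are not reproduced. The point is therefore limited to the protocol as available. That the quota does not reach the 15 is read from silence, not from a statement.
- **These endpoints are informational.** This is correct. They are labelled so, the evaluation is called limited, and no hypothesis test is planned. It bounds the weight of the point, but an acceptance criterion is still attached to the results.
- **Normal use is wider than the subset.** This also stands. Table 2 schedules observation of the professional's placement with no limit of 15, so Secondary Objective 1 does not rest on the 15 alone.

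Two further readings are tempting. Section 7.1.3 describes enrolled subjects as those who undergo the recordings "and demonstrate the use the application of the electrodes and the ECG on the study subject". One might infer that every subject must perform the task, but the sentence is unclear about who acts and may describe the professional. Only the recruitment script clearly addresses every volunteer, and having all perform the task while scoring 15 is not a contradiction. One might also carry the 40% female minimum into the subset, but the documents do not link sex to dexterity.

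**Conclusion.** The concern holds as a mismatch between the quota's stated purpose and the place where that purpose is measured. Nothing in the available text requires any of the 15 scored users to be 65 or over. Under an assumed random draw from 44 with exactly 14 older, about 5 would be expected, with roughly a one-in-five chance of 3 or fewer. Non-random selection could give fewer, by an amount the documents do not allow one to estimate. If enrolment exceeds the quota, the expected number rises.

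The consequence is confined to what the human-factors results and the dexterity part of Secondary Objective 2 can say about older users. The primary endpoint and the analysis of interpretability by age are not affected. The change is worth making because it is cheap and the older subjects are already being recruited.

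**What to change.** **Preferred.** Complete the subject part of Appendix 30.3.2 for all enrolled subjects. Remove the limit of 15 for the subject measures in the synopsis, section 10.5.2, section 11.5.2 and Appendix 30.3, and add the step to Table 2. The limit can remain for the professional's part. At N = 44 this scores at least 14 older users instead of about 5. The form is completed after the four recordings, so the primary data are not disturbed.

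**Alternative.** Keep the 15, and state in sections 10.5.2 and 11.5.2 and Appendix 30.3.2 that at least 5 of them will be 65 or over and how the 15 are selected. This removes the chance of a very low number, but 5 is close to what a random draw would give on average, so it adds less information than the preferred option.

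**In either case.** Report the subject human-factors results separately for subjects under 65 and those 65 or over.

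**Cost.** The preferred option takes a few minutes of coordinator time for each extra subject (44 − 15 = 29 at the planned size), on a task volunteers are already told to expect. The alternative only constrains which 15 are assessed. Neither adds subjects or visits.

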## 2.0 Introduction and Background

For over 20 years, novel devices for ambulatory heart rhythm monitoring have emerged and begun to be integrated with the care of the cardiac patient in the outpatient setting. The evolution of these cardiac monitoring devices will mark a new era in medicine and a transition from population-level health care to individualized medicine in which suitable patients are equipped with advanced biosensors that, in turn, have their data processed through sophisticated algorithms to predict events before they occur.

There are multiple purposes for the various heart rhythm monitoring devices that exist to date. Some monitor ECG rhythms for 30 seconds (Emay), some are used to determine normal sinus rhythm versus atrial fibrillation (Kardio-Mobile), others monitor ECG and blood pressure (Omron), or 12-Lead ECG (Biocare), the Zio Patch(iRhythm), and the S-Patch Ex Wearable ECG Patch (Wellysis Corporation).

Seers Technology Company, Ltd. seeks regulatory clearance to marketing in the U.S. for the mobiCARE™ ECG Monitoring Device. The mobiCARE™ System is an ECG recorder including four models that record ECG for up to 9 days: MC200M, MC200ML, MC200M7, and MC200ML7. The devices will be prescribed by a healthcare professional and will be used by patients both at home and in clinical settings.

The commercial use of the mobiCARE™ ECG Monitoring System in thousands of Korean patients has previously demonstrated the safety of the mobiCARE™ system. Additionally, multiple studies have been completed and published in the Republic of Korea using the Seers Technology Company, Ltd. mobiCARE™ device and its predecessor, MC100. This study will be conducted to demonstrate interpretability and usability, as described in the purpose below.

## 3.0 Purpose

The purpose of the Seers Technology Company Ltd. sponsored study using the mobiCARE™ ECG Monitoring System is to document the variability and interpretability of heart rhythm tracings from the nominal position whereby the mobiCARE™ device is still able to obtain interpretable ECG signals, in a cohort of adults representative of the U.S. population.

Informational data will be collected, such as P-wave amplitude and QRS amplitude and duration to note any morphological ECG signal changes. Human factors (HF) endpoints will be evaluated including: HCP placement according to IFU, subject demonstration of changing electrodes, dexterity for user to perform the task, electrode placement according to skin markings, and the ability of the user to remove and replace the mobiCARE™ device.

## 4.0 Device Description - Intended Use - Indication for Use

**Description:** mobiCARE™ MC200M/mobiCARE™ MC200ML (hereinafter mobiCARE™ MC200M series) is single channel, wearable, mobile and reusable ambulatory ECG recorder. It can continuously acquire and store ECG signals through disposable electrodes for more than 6 or 9 days (expected continuous measurement time is different by the model). The mobiCARE™ MC200M series is not intended for real time monitoring.

**Indications for Use:** The mobiCARE™ Cardiac Monitoring System is indicated for use on patients who may be asymptomatic or who may suffer from transient symptoms such as palpitations, shortness of breath, dizziness, light headedness, pre-syncope, syncope, fatigue, chest pain and/or anxiety. mobiCARE™ Cardiac Monitoring System is intended for use by patients 18

years or older. The device is not intended for use with critical care patients or for real-time monitoring.

## 5.0 Study Design

Prospective, non-randomized, single-center non-significant risk study.

### 5.1 Population

The study population will include adults who are asymptomatic or who may suffer from transient symptoms such as arrhythmias and/or palpitations, shortness of breath, dizziness, light headedness, pre-syncope, syncope, fatigue, chest pain and/or anxiety; ranging in age, ethnic group, BMI, educational level and gender.

### 5.2 Eligibility Criteria

#### 5.1.1 Inclusion Criteria

All answers must be YES to the Inclusion Criteria below:

1. Male and female adults  $\geq$  18 years of age;
2. Willing and able to provide informed consent;
3. Able to speak and read English fluently;
4. Participant is ambulatory.

#### 5.1.2 Exclusion Criteria

All answers must be NO to the Exclusion Criteria below:

1. Patients with cardiac pacemaker;
2. Patients with cardioverter defibrillator;
3. Patients with other implantable electric devices;
4. Currently or has a medical history of skin cancer, rash, skin disorder, keloid, and/or any injury in the chest area;
5. Patients with symptomatic episodes where variations in cardiac performance could result in immediate danger to the patient;
6. Patients with known history of life-threatening arrhythmias;
7. Use in combination with external cardiac defibrillators or high frequency surgical equipment near strong magnetic fields or devices such as MRI;
8. Patients with neuro-stimulator, as it may disrupt the quality of ECG data;
9. Critical care patients;
10. Chest pain at the time of presentation for the study.

